4.3 General Variables

4.3.1 Study Day Definitions

Study day 1 is defined as the date of first dose of study treatment.

For visits (or events) that occur on or after first dose of study treatment, study day is defined as (date of visit [event] – date of first dose of study treatment + 1). For visits (or events) that occur prior to first dose, study day is defined as (date of visit [event] – date of first dose of study treatment). There is no study day 0 defined for this study.

For listings (such as for AEs) that include the derivation of “days since last dose”, this is defined as (event date – date of last dose) where “date of last dose” is defined as the date of dosing immediately preceding the event occurrence. Events that occur on the same day as the last dose of study treatment will therefore be described as occurring zero days from last dose of study treatment.

4.3.2 Time Windows

A windowing convention will be used to determine the analysis value for a given study visit for visit-based assessments, which are as follows:

- serum sample for AZD7442 pharmacokinetic assessments (PK)
- serum sample for AZD7442 anti-drug antibodies (ADA) assessments
- serum sample for **CCI** [REDACTED]
- clinical chemistry, hematology, coagulation and urinalysis
- vital signs
- electrocardiogram (ECG)

The window for the visits following baseline will be constructed in such a way that the upper limit of the interval falls halfway between the two visits (the lower limit of the first post-baseline visit will be Day 2). If an odd number of days exists between two consecutive visits, then the upper limit will be taken as the midpoint value minus 1 day.

One or more results for a particular variable may be obtained in the same visit window. In such an event, the result with the date closest to the expected visit date will be used in the analysis. In the event that two observations are equidistant from the expected visit date, the later observation will be used in the analysis.

The visit windows are defined in the following tables.

Table 1a: Time window for serum sample for AZD7442 pharmacokinetic assessments

Visit	Day Relative to Dose	Visit Window (Study Day)
Day 1	≤ 1	≤ 1
Day 2	2	2 — 3
Day 5	5	4 — 6
Day 8	8	7 — 11
Day 15	15	12 — 18
Day 22	22	19 — 26
Day 31	31	27 — 45
Day 61	61	46 — 75

Parexel International

AstraZeneca

D8850C00009

Statistical Analysis Plan

Day 91	91	76 — 135
Day 181	181	136 — 225
Day 271	271	226 — 315
Day 361	361	≥316

Table 1b: Time window for serum sample for AZD7442 anti-drug antibodies

Visit	Day Relative to Dose	Visit Window (Study Day)
Day 1	≤ 1	≤ 1
Day 31	31	15 — 60
Day 91	91	61 — 135
Day 181	181	136 — 270
Day 361	361	≥271

Table 1c: Time window for serum sample for CCI

CCI		
		
		
		
		
		
		
		
		

CCI		
-----	--	--

Table 1d: Time window for clinical chemistry, hematology, coagulation, urinalysis, vital signs and ECG

Visit	Day Relative to Dose	Visit Window (Study Day)
Screening	≤ 1	≤ 1
Day 1	1	1
Day 5	5	2 — 6
Day 8	8	7 — 19
Day 31	31	20 — 196
Day 361	361	≥ 196

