Serum sample for CCI [REDACTED] ^m		X
AstraZeneca Thank you Card		X

- ^a Update of the screening medical history and physical examination (any new findings since screening).
- ^b Serum chemistry, hematology, coagulation, FSH, urinalysis, urine drug, and alcohol screen do not need to be repeated on Day 1 as per investigator's discretion, if they were performed within 2 days prior to Day 1. Serum chemistry, hematology and coagulation may be repeated only once during Screening period, if values at Screening visit were outside of reference range and documented as not clinically significant.
- ^c Female participants only. Pregnancy test must be negative at screening as well as before randomization and study drug administration.
- ^d Urine dipstick pregnancy test will be done on female participants of childbearing potential only (not postmenopausal female participants that will be identified based on FSH test).
- ^e On Day 1, alcohol breathalyzer test needs to be performed before randomization if urine alcohol screen was done more than 2 days before Day 1. If alcohol breathalyzer test is positive, participant cannot be included in the study.
- ^f SAE data will be collected from screening until Day 361. AE data will be collected from Day 1 until Day 361.
- ^g Participants will be asked about anti-COVID-19 vaccination status. Participants should be either non-vaccinated or vaccinated (with one or more locally approved/authorized COVID-19 vaccine dose) with the last dose of the vaccine received at least 14 calendar days before Day 1. Vaccination status will be entered into IRT/RTSM during randomization on Day 1 visit to allow for balanced recruitment.
- ^h SARS-CoV-2 RT-PCR test or a rapid SARS-CoV-2 antigen test will be done at a local laboratory/site. If a documented SARS-CoV-2 RT-PCR test is not available at screening, a rapid SARS-CoV-2 antigen test will be performed on the day of randomization, pre-dose (for screening criteria). Either test must be negative before dosing.
- ⁱ SARS-CoV-2 serology analysis will be done at the central laboratory for all participants.
- ^j Participants will be randomized in a 1:1:1 ratio by site of injection to receive the IM dose of the IMP in the lateral thigh, gluteal dorsal or gluteal ventral. This information will be provided to the investigator via IRT/RTSM. Participant should be monitored for injection site reaction on Day 1.

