- ^k On Day 1 PK samples will be collected at pre-dose, and then 2 h, 4 h, and 8 h post dosing; on Day 2 PK sample will be collected 24 h post dosing.
- ^l On Day 1 sample will be collected as pre-dose only.
- ^m On Day 1 samples will be collected as pre-dose and then 2 h and 4 h post dosing; on Day 2 sample will be collected 24 h post dosing.

Abbreviations: AE: adverse event; β -hCG: beta human chorionic gonadotropin; BMI: body mass index; ECG: electrocardiogram; FSH: follicle-stimulating hormone; HIV: human immunodeficiency virus; IRT/RTSM Interactive Response Technology/Randomization and Trial Supply Management; PK: pharmacokinetics; SAE: serious adverse events; RT-PCR: reverse transcriptase polymerase chain reaction; SAE: serious adverse event; SARS-CoV-2: Severe Acute Respiratory Syndrome Corona Virus 2.

Table 3-2 Schedule of Assessments: Follow-up Period

Procedures	Follow-up Period										
Study Day	Day 2	Day 5 ±1 day	Day 8 ±1 day	Day 15 ±1 day	Day 22 ±2 days	Day 31 ±2 days	Day 61 ±5 days	Day 91 ±5 days	Day 181 ±5 days	Day 271 ±7 days	Day 361/ET ±7 days
Study Visit	Visit 3	Visit 4	Visit 5	Visit 6	Visit 7	Visit 8	Visit 9	Visit 10	Visit 11	Visit 12	Visit 13
Full physical examination, height, weight, and BMI			X			X					X
12-Lead ECG		X	X			X					X
Vital signs		X	X			X					X
Serum chemistry		X	X			X					X
Hematology		X	X			X					X
Coagulation		X	X			X					X
Urinalysis		X	X			X					X
Pregnancy test (urine dipstick) ^a	X	X	X	X	X	X	X	X	X	X	X
Assessment of AEs/SAEs	X	X	X	X	X	X	X	X	X	X	X
Concomitant medications	X	X	X	X	X	X	X	X	X	X	X
Anti-COVID-19 vaccination status ^b	X	X	X	X	X	X	X	X	X	X	X
Monitoring for COVID-19 symptoms and exposure history	X	X	X	X	X	X	X	X	X	X	X
Serum sample for AZD7442 PK	X	X	X	X	X	X	X	X	X	X	X
Serum sample for anti-AZD7442 antibodies						X		X	X		X
Serum sample for CCI [REDACTED]	X		X			X	X	X	X	X	X
SARS-CoV-2 serology	X		X			X	X	X	X	X	X

^a For female participants only. Pregnancy test should be negative for continued participation in the study.

^b Participants will be allowed to receive anti-COVID-19 vaccination during the study, however, should wait 14 days after their dose of AZD7442, and will be asked about the vaccination status at each visit. Participant vaccination status will be documented throughout the study in the eCRF.

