6.6. Immunogenicity Assessments

Blood samples for determination of serum anti-AZD8895 and anti-AZD1061 antibodies will be analyzed by PPD on behalf of AstraZeneca, using a validated assay. Blood samples for

determination of these ADAs will be collected as specified in the SoA ([Table 3-1](#) and [Table 3-2](#)). Unscheduled samples for ADA analysis should be collected in response to suspected immune-related AEs.

If a participant's sample at the last study visit is confirmed ADA positive, the participant may be asked to return to the clinic for additional sampling if judged necessary by the AstraZeneca Lead Physician and the PI.

Samples will be collected, handled, labeled, stored, and shipped as detailed in the Laboratory Manual.

The presence or absence of ADA will be determined in the serum samples using a validated bioanalytical method. A tiered testing scheme will be employed, with the first step being screening. Samples found positive in the screening step will be tested in the confirmatory step. Samples confirmed positive for ADA in the confirmatory step will undergo endpoint titer determination.

Full details of the analytical method and analyses performed will be described in a separate bioanalytical report.

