4.11.5 Laboratory assessments

Hematology and clinical chemistry values will be listed by participant and time point including changes from baseline and repeat/unscheduled measurements. Summary tabulations will be presented by treatment group, which will exclude unscheduled measurements. The baseline for the measurements will be the pre-dose assessment on Day 1. Shift tables will also be presented, and will consider unscheduled assessments.

The listings will include the following information: test name, date of measurement, reference range, result and flags for any measurements that are outside the reference range (eg, AstraZeneca, program, or laboratory ranges). Clinical laboratory data will be reported in System International units in the CSR.

Additional listings will be presented for the following:

- Urinalysis (macroscopic and microscopic, if applicable)
- Pregnancy testing (including FSH)
- The results of viral serology and the drugs of abuse and alcohol screen will not be listed in the CSR.

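### SAP laboratory-baseline and visit-window rules conflict with each other or with the protocol; the effect is confined to secondary safety and by-visit tables

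*SAP*

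**What the plan says.** **Laboratory baseline.** SAP 4.11.5 states "The baseline for the measurements will be the pre-dose assessment on Day 1", and Protocol 10.1.2 agrees. Protocol Table 3-1 footnote b lets the investigator omit Day 1 chemistry, hematology, coagulation and urinalysis "if they were performed within 2 days prior to Day 1". SAP 4.2 defines baseline for change scores as the last reliable value before the first dose, not limited to Day 1.

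**Visit windows.** SAP 4.3.2 opens with "A windowing convention will be used to determine the analysis value for a given study visit for visit-based assessments", and its list covers PK, ADA, laboratory, vital-sign and ECG data. Each upper limit lies halfway to the next visit, less 1 day when an odd number of days lies between the two visits, and "the lower limit of the first post-baseline visit will be Day 2". Table 1d prints Day 31 as 20–196 and Day 361 as 196 onward. Table 1b goes from Day 1 (up to 1) to Day 31 (15–60).

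**Several results in one window.** By SAP 4.3.2, "the result with the date closest to the expected visit date will be used in the analysis"; for ties, "In the event that two observations are equidistant from the expected visit date, the later observation will be used in the analysis".

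**Samples these rules touch.** Protocol 6.6 says "Unscheduled samples for ADA analysis should be collected in response to suspected immune-related AEs". Protocol Table 3-1 footnote k says "On Day 1 PK samples will be collected at pre-dose, and then 2 h, 4 h, and 8 h post dosing".

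**The concern.** SAP section 1 says that the document outlines the programming specifications, so its rules should lead two programmers to the same tables. Here they do not.

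- A participant whose Day 1 chemistry and hematology were properly omitted has a baseline under SAP 4.2 and none under SAP 4.11.5.
- A record on study Day 196 belongs to two visits.
- An ADA sample drawn on Days 2–14 belongs to none.
- The four Day 1 PK samples meet a one-value-per-window rule with no stated exemption.

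At stake are the laboratory change-from-baseline and shift tables, some by-visit safety rows, the by-visit ADA table and, if the PK point were misread, the Day 1 concentration summaries.

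**Working it through.** **1. Reproducing the printed windows.** Inputs are the visit days and limits in SAP Tables 1a, 1b and 1d. (Table 1c is redacted and was not checked.) For adjacent visits d1 and d2, the midpoint is (d1 + d2)/2 and the number of days strictly between is d2 − d1 − 1. If that number is odd, the upper limit is the midpoint − 1; if even, it is the half-day midpoint rounded down. Each next window starts 1 day later, and the first starts on Day 2.

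- Table 1a: the rule gives 2–3, 4–6, 7–11, 12–18, 19–26, 27–45, 46–75, 76–135, 136–225, 226–315 and ≥316. All 11 rows match.
- Table 1b: the rule gives 2–60, 61–135, 136–270 and ≥271. Three of 4 match; the first is printed as 15–60.
- Table 1d: the rule gives 2–6, 7–19, 20–195 and ≥196. Three of 4 match; the third is printed as 20–196.

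So 17 of 19 post-baseline rows reproduce. Reading the odd-number clause as the difference d2 − d1 fails on the SAP's own table: 61 − 31 = 30 is even, which would give 46, but Table 1a prints 45.

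**2. Day 196.** Days strictly between Day 31 and Day 361: 361 − 31 − 1 = 329, odd. Midpoint: (31 + 361)/2 = 196. Upper limit: 196 − 1 = 195. Day 196 is the only post-baseline day in two windows, and it is equidistant: 196 − 31 = 165 and 361 − 196 = 165. The tie rule does not help, because it chooses between two observations for one visit, not between two visits for one observation.

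**3. ADA, Days 2–14.** Unassigned days: 14 − 2 + 1 = 13. Protocol Table 3-2 schedules no ADA sample there, so only unscheduled samples (Protocol 6.6) or an early-termination visit, which repeats the Day 361 assessments (Protocol 5.7.1), can fall in the gap. SAP 4.10.5.2 summarises ADA results and titers by visit and does not exclude unscheduled samples. Starting the window at Day 2 closes the gap but does not ensure that an early result is shown. A sample from Days 2–14 is 31 − 14 = 17 to 31 − 2 = 29 days from Day 31. A routine sample taken in its ±2-day allowance is at most 2 days away, so the closest-date rule keeps the routine one.

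**4. Laboratory baseline.** Take a participant tested on Day −1 or Day −2 and not retested on Day 1.

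| Rule | Baseline |
|---|---|
| SAP 4.2 | the Day −1 or −2 value |
| SAP 4.11.5, Protocol 10.1.2 | none, since there is no Day 1 value |

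Table 1d does not bridge the two, because it assigns that result to Screening and limits the Day 1 window to Day 1. SAP 4.3.3 generally leaves missing data unimputed, so under 4.11.5 the change score and the shift entry are missing. The number affected is not given; with 207 planned participants it lies between 0 and 207.

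**5. Day 1 PK samples.** The pre-dose, 2 h, 4 h and 8 h samples are all 0 days from Day 1. Taken alone, the tie rule would keep the 8 h sample. Other provisions point the other way: SAP 4.10.2 summarises each scheduled time point, the mean-profile figures in SAP 4.10.4 use planned nominal time, and SAP 4.5.3 relies on the pre-dose concentration for its 5%-of-Cmax check. SAP 4.3.3.3 bases PK analysis on actual elapsed times.

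**The case against.** The strongest reply is that a competent programmer would resolve all of this, and that the TFL shells, to which SAP 4.2 defers further programming detail, may already do so. The shells are not available here. That reply stands for the PK samples, where the specific PK sections leave little doubt.

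On the baseline, it can be said that footnote b lets the earlier test stand in for the Day 1 test, that a value from the preceding 2 days exists whenever a test is omitted, and that Protocol 11.2.1 uses the last pre-dose value when a measurement is repeated. This shows that a usable value exists, but not which rule governs. The laboratory-specific section would normally take precedence, and it names Day 1.

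On the windows, few records are exposed. No laboratory, vital-sign or ECG visit is scheduled near Day 196, and the laboratory and vital-sign summaries exclude unscheduled values (the ECG section does not say so). The Day 15 start for ADA might be deliberate, since a first-week sample says little about Day 31, but then the text is wrong. SAP 4.10.5.2 counts a positive ADA result at any time and lists all ADA results, so nothing is lost at participant level.

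A reader might also see an overlap between Screening and Day 1 in Table 1d, where Screening reads as up to 1. That may be a minus sign lost in reading the PDF, since screening runs from Day −28 to −1, and it is not relied on here.

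**Conclusion.** The point holds as a set of small conflicts between stated rules. The laboratory baseline matters most: under 4.11.5, participants with omitted Day 1 tests drop out of the laboratory change and shift tables; under 4.2 they stay. Table 1d has one day in two windows, and Table 1b leaves 13 days in none. Cmax, AUClast and AUCinf are unaffected, as is participant-level ADA status.

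Two stronger readings are tempting and not supported. A reader might infer that three of every four Day 1 PK samples would be discarded; the PK sections cited above show that they are kept and summarised by scheduled time, so only a clarification is needed. A reader might also infer that participants with omitted tests have no laboratory baseline at all; SAP 4.2 supplies one, and the defect is that two definitions compete.

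The conclusion assumes that the SAP text and tables govern programming and that the unseen shells do not already settle these points.

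**What to change.** 1. In SAP 4.11.5, define the laboratory baseline as the last reliable value before dosing, as in SAP 4.2, and record the departure from Protocol 10.1.2 in SAP 4.14.
2. In Table 1d, set Day 31 to 20–195 and keep Day 361 at 196 onward.
3. In Table 1b, start the Day 31 window at Day 2, to agree with the text. Report ADA results from unscheduled or early-termination samples on Days 2–14 separately, because the closest-date rule would still drop them when a Day 31 sample exists.
4. In SAP 4.3.2, state that the timed Day 1 PK samples are mapped by nominal time and are exempt from the one-value-per-window rule, consistent with SAP 4.10.2.

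The cost is SAP wording, one extra ADA display and minor programming; no new data are needed and the primary analysis does not change. Item 3 has one drawback: without a Day 31 sample, an early result would appear under the Day 31 label, so the table needs a footnote. If the database is already locked, SAP section 1 calls for an addendum and discussion in the CSR.

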4.3.3 Handling of Missing Data

In general, other than for the below described, or where otherwise specified in the particular analysis, missing data will not be imputed and will be treated as missing.

4.3.3.1 Imputations of Partial Dates

Adverse events start dates

- AEs with completely unknown start dates will be imputed with the date and time of dosing, unless the end date is known and prior to dosing; in that case the start date will be imputed as the date of Screening and a time of 00:00.
- AEs with unknown start times, but with start date known, will be imputed with a time of 00:00, unless the start date corresponds to any given dosing date. In this case the start time will be imputed with the time of dosing. If this results in a start date/time after end date/time of the AE, then the time will also be imputed with 00:00.
- Missing day: impute with the 1st of the month, unless the month and year in which the AE started is a month and year in which IMP was administered, then the day will be imputed with the first day on which IMP was administered in that month. If this results in a start date after the end date, then the day will be imputed with the first day of the month.
- Missing month: impute with the 1st month in which IMP was administered. If this results in a start date after the end date of the AE, then the month will be imputed with JAN. If the known

year part is not a year in which IMP was administered, then the month will also be imputed with JAN.

- Missing day and month: impute with the day and month of dosing. If this results in a start date after end date, then the day and month will be imputed with 01JAN. If the year is not a year in which IMP was administered, then the day and month will also be imputed with 01JAN.
- Missing year: impute with the year of dosing.
- Missing times will be imputed as 00:00 h or with the time of dosing for events starting on a dosing day.

When imputing a start date care should be taken to ensure the start date is sensible, i.e., prior to the end date.

Generally, the imputation of dates is used to decide if an observation is treatment emergent for AEs or concomitant for medications. Flags will be retained in the database indicating where any programmatic imputation has been applied, and in such cases, durations and study days will not be calculated.

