10. EVALUATION AND CALCULATION OF VARIABLES

10.1. Safety Variables

10.1.1. Adverse Events

All AEs will be coded using MedDRA vocabulary and will be listed for each participant.

For assigning AEs to a specific treatment/dose, the following guidelines should be followed:

- AEs with start date/time at the time of or after dosing (for each specific treatment/dose) until Follow-Up Visit will be assigned to the specific treatment/dose.
- AEs with unknown start times, but with start date known, will be imputed with a time of 00:00, unless the start date corresponds to any given dosing date. In this case the start time will be imputed with the time of dosing. If this results in a start date/time after end date/time of the AE, then the time will also be imputed with 00:00.
- AEs with completely unknown start dates will be imputed with the date and time of dosing, unless the end date is known and prior to dosing; in that case the start date will be imputed as the date of Screening and a time of 00:00.
- AEs with partially known start dates/times will be treated as follows:
 - If only the day is missing, then the day will be imputed with the first day of the month, unless the month and year in which the AE started is a month and year in which IMP was administered, then the day will be imputed with the first day on which IMP was administered in that month. If this results in a start date after the end date, then the day will be imputed with the first day of the month.
 - If only the month is missing and the year is a year in which IMP was administered, then the month will be imputed with the first month in which IMP was administered. If this results in a start date after the end date of the AE, then the month will be imputed with JAN. If the known year part is not a year in which IMP was administered, then the month will also be imputed with JAN.
 - If both the day and month is missing and the year is a year in which IMP was administered, then the day and month will be imputed with the day and month of dosing. If this results in a start date after end date, then the day and month will be imputed with 01JAN. If the year is not a year in which IMP was administered, then the day and month will also be imputed with 01JAN.
 - If only the year is missing, then the year will be imputed with the year of dosing.
 - Missing times will be imputed as 00:00 h or with the time of dosing for events starting on a dosing day.

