4.11.2 Adverse Events

AEs and SAEs will be collected throughout the study from date of informed consent until the end of the follow-up. MedDRA (using the latest or current MedDRA version) will be used to code the AEs.

Adverse events with onset (start date/time) after dosing will be summarized by treatment group (dose level or administration process of AZD7442, Total AZD7442). Tabulations will include causality (related, not related) and severity (mild, moderate and severe). All tabulations will be presented by MedDRA SOC and PT with the exception of the severity tables, which will be presented by PT only. Furthermore, listings of SAE and AEs that led to withdrawal will be made and the number of participants who had any AE, SAEs, and discontinuation events will be summarized. Adverse Events of Special Interest (related to Anaphylaxis and other serious hypersensitivity reactions, and injections site reactions) will be listed and summarized. The AEs that occur before dosing will be excluded from the summary tables.

Adverse events will be listed by each dose of AZD7442. The following information will be included in the listings: verbatim term, MedDRA SOC, PT and lowest level term, start date/time, end date/time, time from last dose, causality, action taken, whether the AE was classified as serious and the outcome.

All tabulations will include the number and percentage of participants.

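### The missing-year and missing-month rules for adverse-event start dates are not checked against the dosing date, so some post-dose events are dated before dosing and leave the summary tables

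*SAP*

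**What the plan says.** SAP 4.3.3.1 gives one rule for each kind of incomplete AE start date. For the year: "Missing year: impute with the year of dosing". For the month: "Missing month: impute with the 1st month in which IMP was administered", with January used instead when the known year is not a dosing year. Protocol 10.1.1 has the same rules, for example "If only the year is missing, then the year will be imputed with the year of dosing". A start date that is wholly missing is placed at dosing: "AEs with completely unknown start dates will be imputed with the date and time of dosing".

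The general safeguard looks only at the end of the event: "When imputing a start date care should be taken to ensure the start date is sensible, i.e., prior to the end date". The same SAP section says that imputed dates are used to decide whether an AE is treatment emergent.

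SAP 4.11.2 then defines the tables: "Adverse events with onset (start date/time) after dosing will be summarized by treatment group", and "The AEs that occur before dosing will be excluded from the summary tables". Protocol 10.1.1, in its guidance on assigning events to treatment, uses a wider phrase: "AEs with start date/time at the time of or after dosing".

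**The concern.** Each participant has one dose and is then followed for 360 days, so for nearly everyone follow-up runs into the next calendar year. If an AE in that next year lacks only its year, the rule moves it back twelve months, to a date before dosing. If an AE later in the dosing year lacks only its month, it moves to the dosing month and keeps its recorded day. When that day is earlier than the dosing day, the event again becomes pre-dose.

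Both errors remove events from the safety tables, which is the non-conservative direction. That runs against the rest of the plan. SAP 4.3.3.2 treats unknown intensity as severe, unknown relationship as related and unknown seriousness as serious. An AE with no date at all is placed at dosing, while one with a known day and month can be excluded. Safety is a stated secondary objective.

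**Working it through.** The plan states no figure on this point, so there is none to reproduce. I applied the SAP 4.3.3.1 rules to every possible true onset on study days 2 to 361.

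**Inputs from the documents**
- Follow-up: 360 days after dosing (Protocol synopsis). Check: 28 + 1 + 360 = 389 days, the stated total duration.
- Estimated first enrolment November 2021 and last completion Q3 2023 (Protocol synopsis). The second implies last dosing in about Q3 2022.

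**Assumptions**
- Onset is equally likely on each of the 360 days.
- Dosing dates are spread evenly from 15 November 2021 to 30 September 2022. Two other spreads were also run.
- The AE is ongoing or ends after its true onset.

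**Worked examples**
- Missing year: dosed 20 November 2021, true onset 10 February 2022 (study day 83). The imputed start is 10 February 2021, 283 days before dosing.
- Missing month: dosed 20 March 2022, true onset 10 June 2022 (study day 83). The imputed start is 10 March 2022, 10 days before dosing.

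**Formulas by dosing date.** Let r be the number of days from dosing to 31 December. Follow-up is shorter than a year, so every onset in the next calendar year is moved before dosing. The missing-year share is therefore (360 − r)/360. For the missing month, with dosing on day d of month m, onsets on days 1 to d − 1 of each later month of that year are moved before dosing. For the dates below that share is (d − 1)(12 − m)/360.

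| Dosing date | r | Missing year | Missing month |
|---|---|---|---|
| 15 Nov 2021 | 46 | 314/360 = 87.2% | 14 × 1/360 = 3.9% |
| 15 Dec 2021 | 16 | 344/360 = 95.6% | 0% |
| 15 Jan 2022 | 350 | 10/360 = 2.8% | 14 × 11/360 = 42.8% |
| 20 Mar 2022 | 286 | 74/360 = 20.6% | 19 × 9/360 = 47.5% |
| 15 Jun 2022 | 199 | 161/360 = 44.7% | 14 × 6/360 = 23.3% |
| 15 Sep 2022 | 107 | 253/360 = 70.3% | 14 × 3/360 = 11.7% |

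**Averages over dosing dates**

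| Dosing spread | Missing year, before dosing | Missing month, before dosing | Onsets in dosing year | Missing month, dosing-year onsets only |
|---|---|---|---|---|
| 15 Nov 2021 to 30 Sep 2022 | 45.0% | 24.5% | 55.0% | 24.5/55.0 = 44.5% |
| 15 Nov 2021 to 31 Mar 2022 | 39.5% | 27.2% | 60.5% | 27.2/60.5 = 45.0% |
| Full year 2022 | 49.5% | 22.3% | 50.5% | 22.3/50.5 = 44.2% |

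On the first spread, 38.7% of missing-year onsets land more than 28 days before dosing, earlier than the screening period itself. That is 38.7/45.0 = 86% of the misdated ones.

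**Safeguards.** A date moved too early always precedes the end date, so the end-date check never catches these cases.

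**Other rules.** Missing day, missing day and month, and wholly unknown date put 0% before dosing. They set 4.0%, 55.0% and 100% of onsets, respectively, equal to the dosing date.

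**The case against.** The strongest case against is that this will seldom happen and little is lost when it does. The record must have a known day and month without a year, or a known day and year without a month. Participants are asked about health problems since the last enquiry at 11 follow-up visits, which normally fixes the year. Protocol 9.4.1 and 9.5 provide for missing data to be discussed with the investigator and for repeated queries. Listings use unimputed data (SAP 4.3.3.2), imputed records are flagged (SAP 4.3.3.1), and serious AEs and those leading to withdrawal have their own listings. Protocol 11.2.5 says that pre-dose AEs are reported separately. All of this stands, and it limits the size of the problem. It does not make the rules correct.

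A reader might go further and infer that every dosing-day AE without a recorded time, and every undated AE, is dropped, because these are set exactly to the dosing time and SAP 4.11.2 tabulates onset after dosing. The documents do not support that. Protocol 10.1.1 expressly assigns events at the time of dosing to treatment. The exclusion covers only AEs before dosing, and a tie is not before dosing. The protocol also carries the same summary sentence as the SAP, so the two phrases occur within one section and have to be read together. Setting an untimed dosing-day event to the dosing time, not to midnight, makes sense only if ties count. This is a wording inconsistency to reconcile, not a demonstrated loss.

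**Conclusion.** The missing-year and missing-month rules are wrong as written. Among truly post-dose AEs, about 45% of those lacking only the year (39.5% to 49.5% across the spreads tried) would be dated before dosing and left out of the AE summary tables. The same holds for about 25% of those lacking only the month (22.3% to 27.2%), or roughly 44 to 45% of such events in the dosing year.

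These averages rest on uniform onset and on dosing dates inferred from estimated study dates. For a single dosing date the share runs from 0% to 100% for the year and from 0% to 91% for the month. The percentages are not shares of all AEs: they apply only to records lacking exactly that date part, and the documents do not say how many there are. The number is probably small. The effect is confined to the safety summary tables, so this is a minor correction.

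**What to change.** **Rule change.** Add to SAP 4.3.3.1: where the year or the month is missing and the imputed start falls before dosing, use the earliest year or month that puts the start at or after dosing, unless the recorded date parts or the end date show a pre-dose onset. That exception covers, for example, a recorded day before the dosing day when dosing was in December of the known year. By construction, the share of truly post-dose events dated before dosing falls to 0% under both rules.

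**Declaration.** Protocol 10.1.1 contains the same rules, so list this in SAP 4.14 as a change from the protocol. If the database is already locked, SAP section 1 provides for an addendum and discussion in the study report.

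**Wording only.** Align SAP 4.11.2 with the at-or-after phrase in Protocol 10.1.1, so that AEs imputed to the dosing time are clearly counted.

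**Cost.** A few sentences and a small program change. There is one small downside. SAP 4.11.2 collects AEs from consent, so a screening event with no year and no end date could be counted as treatment emergent. For example, with dosing on 20 November 2021, a screening event recorded as 10 November would become 10 November 2022, study day 356. This can arise only for events within the screening period of up to 28 days, and it errs in the conservative direction.
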